8.4 STATISTICAL ANALYSES

8.4.1 General Approach

This is a phase I study. There are two arms to this study for 1) patients with prior prostatectomy, rising PSA, and visible tumor on imaging, and 2) patients with prior prostatectomy with no visible tumor on imaging (rising PSA or indications for adjuvant treatment). Arms are enrolled and escalated separately. Dose level groups of 3-6 patients are evaluated at each dose level. The dose level on which 2 patients experience unacceptable toxicity is considered to have exceeded the MTD. The next lower dose level on which no more than 1/6 patients experience unacceptable toxicity is considered the MTD for each arm of the study.

8.4.2 Analysis of the Primary Endpoints

The primary endpoints will be to define the MTD of this approach.

8.4.3 Analysis of the Secondary Endpoint(s)

- Define the toxicity profile of image-guided, focally dose escalated prostate bed radiation in patients with a local or regional recurrence of prostate cancer after prostatectomy. All AEs except grade 1 with attribution to protocol treatment will be collected in tabulated way and analyzed.
- The rate of PSA control (biochemical progression free survival, bPFS) will be estimated by the Kaplan-Meier survival analysis and effects of clinical variables on bPFS will be assessed by the Cox proportional hazards model.
- The quality of life scores will be summarized at baseline and for each visit. Linear mixed effects model will be used to model quality of life scores at baseline and during and after treatment in which random intercept and random slope are used to account for patient-specific trajectory of quality of life scores. Changes of quality of life scores during and after treatment will be calculated from the estimated linear mixed effect model. The

similar analytical approach will be performed for depression scores and correlated with quality of life scores.

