The volumes targeted by irradiation in the post-prostatectomy setting (adjuvant or salvage) are relatively standard and have been arrived at by consensus [9]. In general, the remaining seminal vesicles, if any, and the bed of the prostate are included. In some cases, a portion of the pelvic lymph nodes are included. Most commonly, this region receives a total dose of 66 to 72 Gy in 1.8- 2 Gy fractions, given daily Monday through Friday, over 6-7 weeks. Although these treatments are delivered on an outpatient basis, they are a substantial investment of time and may require time away from work and incur transportation costs.

In general, the use of adjuvant and salvage radiation is well tolerated, however a subset of patients will develop acute (during or within 90 days of radiation) or late (more than 90 days after completion of radiation) toxicity. Two recently published randomized trials provide estimates of toxicity with contemporary irradiation techniques [7, 10]. Grade 2 or higher acute genitourinary toxicity occurs in approximately 14% of patients, whereas Grade 2 or higher acute gastrointestinal toxicity occurs in 21% of patients (acute Grade 3 or higher GU and GI, 2% and 0.5% respectively). Grade 2 or higher late genitourinary toxicity occurs in approximately 25% of patients, whereas Grade 2 or higher late gastrointestinal toxicity occurs in 18% of patients (late Grade 3 or higher GU and GI, 7% and 2% respectively).

Radiation is often combined with androgen deprivation therapy (ADT) in patients with prostate cancer treated with salvage radiation after prostatectomy (detectable PSA). Two recently reported randomized trials of salvage radiation after prostatectomy delivered with or without ADT have shown a benefit in progression free survival or overall survival [7, 10]. These trials demonstrated no increase in bowel or bladder toxicity with the addition of ADT to radiation compared to radiation alone. Based on these results, the use of ADT with radiation is considered appropriate in some, but not all, patients receiving salvage radiation. The use of ADT is dependent of specific tumor and patient characteristics, including age, comorbidity, PSA at the time of radiation, Gleason score, margin status, presence of extra prostatic extension, and patient willingness. We will allow patients to receive ADT on this trial if deemed clinically appropriate,

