3.1.1 Dose Limiting Toxicity

The DLT period includes treatment period (4, 3 or 2 weeks depending on Dose Level) and the 3 following weeks. DLT is defined as any of the following:

- Grade 3 rectal, small bowel, or urinary toxicity that does not resolve to Grade 2 or less within 4 days with appropriate medical management.
- Other grade 3 in-field toxicities attributable to RT that do not resolve to Grade 2 or less within 4 days with medical management.
- Delays of more than one week in completing radiation treatment due to toxicity (cumulative duration of delay over the course of the entire treatment).

Additionally, toxicities that occur more than 3 weeks after completion of treatment and during the 24 month follow up period will be followed and scored but will not be used for escalation with the following exception. If Grade ≥ 4 late bowel or bladder injury is observed in 2 patients at any Dose level, dose escalation will be terminated and the dose below that dose level in which the toxicity was observed will be considered the MTD. Early and late toxicities used for assessment of DLTs should be attributable (possible, probable or definite) to radiation. Changes in sexual and erectile function will not be considered a DLT. MTD will be determined for each Arm separately.

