8.4.4 Safety Analyses

Adverse events will be coded as per the CTCAE v4.0. Each AE will be coded once for each patient based on the maximum severity during the assessment period. The relationship of AEs to study intervention will be recorded in addition to the onset date, end date, severity, expectedness, and outcome.

Dose-limiting toxicities are defined as follows (during treatment and within the first three weeks after treatment):

- Grade 3 rectal, small bowel, or urinary toxicity that does not resolve to Grade 2 or less within 4 days with medical management
- Other grade 3 in-field toxicities attributable to radiation that do not resolve to Grade 2 or less within 4 days with medical management
- Delays of more than one week in completing radiation treatment due to toxicity (cumulative duration of delay over the course of the entire treatment).

Additionally, toxicities attributable to radiation after the DLT assessment period (3 weeks after radiation is completed) will be followed and scored but will not be used for escalation with the following exception. If Grade ≥ 4 late bowel or bladder injury (late toxicity is defined as occurring >90 days after completion of radiotherapy) is observed in 2 patients in any Dose level group, dose escalation will be terminated and the dose below that dose level in which the toxicity was observed will be considered the MTD. Early and late toxicities used for assessment of DLTs should be attributable (possible, probable or definite) to radiation. Sexual and erectile dysfunction as a result of radiation will not be considered a DLT. Note that MTD will be determined for each Group separately.

Dose-limiting toxicities are defined as per section **3.1.1**.

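### Late toxicity over 24 months is to be tabulated with no account of follow-up time, which would modestly understate late rates if men leave early

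*Combined protocol and SAP*

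**What the plan says.** Section 3.1.1 provides that toxicities arising more than 3 weeks after treatment and "during the 24 month follow up period will be followed and scored". Section 8.4.4 defines late as more than 90 days after radiotherapy.

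The analysis is given in two places. Section 8.4.3 says that attributable adverse events, apart from grade 1, "will be collected in tabulated way and analyzed". Section 8.4.4 says: "Each AE will be coded once for each patient based on the maximum severity during the assessment period". The assessment period is not defined for late events. Neither section names an estimator, a censoring rule, a minimum follow-up or a data-cut date for late toxicity.

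The data for a time-based analysis are foreseen: the relationship of each event to treatment "will be recorded in addition to the onset date, end date, severity, expectedness, and outcome". The method is also already in the plan, because the biochemical progression-free survival rate in the same men "will be estimated by the Kaplan-Meier survival analysis".

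Section 3.7.2 takes men off study for recurrence, withdrawal, death, non-compliance and loss to follow-up, among other reasons. Sections 8.3 and 8.3.1 exclude from the toxicity population only men removed from protocol treatment for a reason other than a DLT. Section 6.1 says that beyond 30 days after the last treatment only serious, related adverse events have to be recorded.

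**The concern.** Late toxicity builds up between month 3 and month 24. A man who completes radiation and is last seen at month 4 is not covered by the exclusion in section 8.3.1, so he stays among the treated men. In a plain table he cannot be told apart from a man followed for 24 months without an event. If percentages are then taken over all treated men, the late rates come out too low.

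The précis says the schedule is designed to give late toxicity similar to standard treatment, and section 1.2.1 supplies the historical figures a reader will set beside the results. For example, "Grade 2 or higher late genitourinary toxicity occurs in approximately 25% of patients". A late rate with no stated follow-up cannot be read against such a figure.

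**Working it through.** **The plan's own figures.** No precision, exit rate or target rate is stated for late toxicity. The related figure is the sample size in section 8.2, which reproduces: 3 levels × 6 men + 6 expansion = 24 per arm, and × 2 arms = 48.

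**Inputs from the documents.** Late Grade 2+ rates of 25% (GU) and 18% (GI), section 1.2.1; late window from 90 days (about month 3) to month 24, sections 3.1.1 and 8.4.4.

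**Assumptions.** Section 1.2.1 gives no time horizon for its rates; they are taken here as true 24-month incidences. The hazard of late toxicity is constant from month 3 to month 24. Exit has a constant hazard, is independent of toxicity, and totals 10%, 20% or 30% by month 24. The documents give no exit rate.

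**Formulas.** With p the true 24-month rate and d the proportion leaving by month 24:

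- toxicity hazard λ = −ln(1 − p)/21
- exit hazard μ = −ln(1 − d)/24
- crude proportion = exp(−3μ) × λ/(λ + μ) × [1 − exp(−21(λ + μ))]

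**Worked case, p = 25%, d = 20%.** λ = 0.28768/21 = 0.01370; μ = 0.22314/24 = 0.00930. The crude proportion is 0.9725 × 0.5957 × 0.3830 = 0.222.

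| Assumed exit by month 24 | Crude GU (true 25%) | Crude GI (true 18%) | Expected GU cases missed in 6 men | Expected GU cases missed in 24 men |
|---|---|---|---|---|
| 0% | 25.0% | 18.0% | 0 | 0 |
| 10% | 23.6% | 17.0% | 0.08 | 0.33 |
| 20% | 22.2% | 16.0% | 0.17 | 0.67 |
| 30% | 20.7% | 14.9% | 0.26 | 1.03 |

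Cases missed are n × (true rate − crude rate); for example, 24 × (0.2500 − 0.2069) = 1.03. Events clustered early in the window would shrink the bias, and events clustered late would enlarge it. Under the same assumptions, an estimate that censors at last assessment targets the true 25% or 18%.

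**Dose levels.** If every man has reached month 24 or left, and exit is the same at each level, the crude GU rate is the same at each level: 25% with no exit, 22.2% with 20% exit. A gradient needs an earlier analysis or unequal exit.

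**Recording.** Sections 3.1.1 and 8.4.4 follow and grade toxicity after the DLT period. Section 6.1 does not require a non-serious event to be recorded after day 30. A non-serious late Grade 2 or 3 event, and its onset date, could therefore be missing. That would affect any late-toxicity analysis, and possibly more than the choice of estimator does.

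**The case against.** The best defence has four parts.

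- **The method is open, not wrong.** The sentence in section 8.4.3 says the events will also be analysed. A reader might infer that the plan counts early leavers as free of toxicity. It does not say so: no late-toxicity percentage or denominator is specified, and men removed from treatment early for non-DLT reasons are excluded (8.3.1) and replaced (3.1.2). Nor does the plan keep a single record per man; it keeps one per event per man. The bias follows only if crude proportions over treated men are reported. This stands, but an unnamed method does not close the gap.
- **The effect is small beside sampling error.** The exact 95% interval is 0.4% to 64% for 1 of 6, and 10% to 47% for 6 of 24. This stands, and it argues against separate curves for each dose level. The plan also limits loss of data through three-monthly remote contact (3.3) and documented attempts to reach men who miss visits (3.7.3).
- **No late-toxicity comparison is planned.** The objective is to describe safety. This also stands, although readers will still set the rates beside the historical ones.
- **The dose-level effect is speculative.** A reader might infer that the last-enrolled, most hypofractionated level will look safest. If levels enrolled in successive 10-month blocks with about one month of treatment, no exits and equal true risk, a cut 12 months after the last enrolment would give crude rates of 25.0%, 24.5% and 16.2% at Levels 1, 2 and 3. The documents support neither that schedule nor that cut. The arms escalate independently, the six-man expansion at the MTD may enrol last and at a lower level, and no analysis before month 24 is planned, though none is ruled out.

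**Conclusion.** The point holds as a recommended improvement. The plan follows toxicity for 24 months and states no analysis that uses follow-up time, although it collects onset dates and applies a time-to-event method to another endpoint in the same men. If crude proportions over treated men are reported, a true 25% reads as 23.6%, 22.2% or 20.7% at an assumed 10%, 20% or 30% exit. At 30% exit that is about one expected case in a full 24-man arm and about a quarter of a case in a six-man level. These sizes rest on the assumed exit rates, the constant hazards and the reading of the historical 25% as a 24-month figure. With complete follow-up there is no bias. Distortion between dose levels is possible but conditional. The MTD rules are not affected.

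**What to change.** In sections 8.4.3 and 8.4.4:

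- **Per arm:** estimate late (more than 90 days) Grade 2+ and Grade 3+ GU and GI toxicity as cumulative incidence at 12 and 24 months from the end of radiation, using recorded onset dates. Censor at the last toxicity assessment, including for men who leave at recurrence, and treat death as a competing event. Give numbers at risk and 95% confidence intervals. State the assumption that censoring, notably at recurrence, is unrelated to toxicity risk.
- **By dose level** (3 to 6 men, up to 12 at the MTD): keep the maximum-grade table as a description, with follow-up time or numbers at risk beside the counts.
- **Timing:** run the final late-toxicity analysis once every man has reached month 24 or left the study.

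Reconcile section 6.1 with sections 3.1.1 and 8.4.4 so that non-serious late Grade 2 and 3 events and their onset dates are recorded.

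The sample size and escalation rules do not change. The cost is a few sentences, slightly more analysis work, and possibly more recording than section 6.1 now requires. The intervals will be wide, and the late rates will look slightly less favourable.

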1.1.2 Secondary Objectives

- To evaluate the safety and tolerability of the image guided, hypofractionated, focally dose escalated post-prostatectomy radiation.
- Estimate the rate of PSA control (biochemical progression free survival (bPFS) at 1 and 2 years after treatment with image guided, hypofractionated, focally dose escalated post-prostatectomy radiation).
- Describe the effects of image-guided, focally dose escalated prostate bed radiation on patient reported outcomes (SHIM, AUA Symptom Index, EPIC-26).

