- The Expanded Prostate Cancer Index Composite (EPIC-26) is a prostate cancer health-related quality of life (HRQOL) patient self-administered instrument that measures urinary, bowel, sexual, and hormonal symptoms related to radiotherapy and hormonal therapy. The EPIC-26 was developed from the 50-item EPIC questionnaire and was validated using question responses from 252 subjects who had undergone brachytherapy, external beam radiotherapy, or prostatectomy for prostate cancer. A high correlation was observed between the EPIC-50 and EPIC-26 versions for the urinary incontinence, urinary irritation/obstruction, bowel, sexual, and vitality/hormonal domain scores (all $r >= 0.96$). The correlations between the different domains were low, confirming that EPIC-26 retained the ability to discern the distinct HRQOL domains. The internal consistency and test-retest reliability for EPIC-26 (Cronbach's alpha $>= 0.70$ and $r >= 0.69$, respectively for all HRQOL domains) supported its validity. EPIC-26 has been used in multiple RTOG protocols and phase II publications for hypofractionated radiotherapy to the prostate.
- Sexual Health Inventory for Men (SHIM) is a prostate specific questionnaire for assessment of erectile dysfunction. Initially derived from the IIEF, a shortened version to six questions the IIEF-6 or SHIM was created for increased usability in the clinic.

- American Urologic Association Symptom Index Score (AUA-SI) has been established as a measure of radiation morbidity in patients treated for prostate cancer with respect to urinary function and is used routinely as the basis for treatment decisions. Moderate agreement was observed between EPIC domains and the American Urological Association Symptom Index (AUA-SI), providing criterion validity without excessive overlap.
- PROMIS – Depression SF4a: The PROMIS Depression item bank assesses self-reported negative mood (sadness, guilt), views of self (self-criticism, worthlessness), and social cognition (loneliness, interpersonal alienation), as well as decreased positive affect and engagement (loss of interest, meaning, and purpose). The depression short forms are universal rather than disease-specific. All assess depression over the past seven days. PROMIS instruments are scored using item-level calibrations.

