4.1 ADT

We will allow patients to receive ADT on this trial after enrollment if deemed clinically appropriate, as the bulk of data suggests that it has no impact on the toxicities we have defined as DLTs in this trial.

ADT will be delivered on this protocol as per the current standard of care with the duration of therapy to be determined by the treating physician if indicated. This may include an anti-androgen, gonadotropin releasing hormone agonist, or the combination of both. As an alternative, patients may also receive ADT through their local care provider (medical oncologist, primary care physician, urologist) in collaboration with the research team.

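### Section 8.4.3 gives no ADT term, stratum or display for SHIM and the EPIC-26 sexual and hormonal domains, so change in these scores would combine ADT with radiation

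*Combined protocol and SAP*

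**What the plan says.** The secondary objective in section 1.1.2 is to "Describe the effects of image-guided, focally dose escalated prostate bed radiation on patient reported outcomes", naming SHIM, the AUA index and EPIC-26. Section 8.1.2 adds the hypothesis that erectile dysfunction worsens over time and does not improve.

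The analysis in section 8.4.3 is: "Linear mixed effects model will be used to model quality of life scores at baseline and during and after treatment". Each man has a random intercept and slope, and changes are calculated from the fitted model. Clinical variables are mentioned in that section only for the Cox model of biochemical progression-free survival.

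Section 4.1 allows ADT after enrollment, "with the duration of therapy to be determined by the treating physician if indicated". The reason given is "as the bulk of data suggests that it has no impact on the toxicities we have defined as DLTs in this trial". The evidence in section 1.2.1 is that two randomised trials found "no increase in bowel or bladder toxicity with the addition of ADT to radiation compared to radiation alone". Section 3.1.1 states: "Changes in sexual and erectile function will not be considered a DLT". Section 1.2.3 says EPIC-26 "measures urinary, bowel, sexual, and hormonal symptoms related to radiotherapy and hormonal therapy".

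For MRI of erectile tissue, section 5.1.4 plans separate evaluation of men with and without ADT. Footnote 6 of the study calendar asks for a questionnaire before ADT starts. It asks for a second one in the week before radiation only when ADT began more than a month before radiation.

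**The concern.** The objective attributes score change to radiation. ADT can also change sexual and hormonal scores, and its use, timing and duration will differ between men over the 24 months. The reason for allowing ADT covers the toxicities counted as DLTs. Sexual and erectile change is outside that definition, so the reason does not extend to SHIM or the EPIC-26 sexual domain, and the evidence cited is on bowel and bladder.

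The protocol separates ADT for an exploratory imaging endpoint, but not for the secondary endpoint that measures sexual function directly. At stake is how the reported change in three scores is read (SHIM, EPIC-26 sexual and EPIC-26 hormonal), and with it the erectile hypothesis of section 8.1.2.

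**Working it through.** **The plan's own figure.** Section 8.2 gives a maximum of 48. This reproduces: 2 arms × (3 dose levels × 6 + 6 expansion) = 2 × 24 = 48. No effect size, SD or power is stated for the questionnaire scores.

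**Formula.** Take a lower score as worse. Let d be the drop in score, in SD, while a man is under ADT effect. At any visit:

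pooled change = radiation change − d × (share under ADT effect at the visit − share under ADT effect at the baseline form)

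The second term is zero if nobody has ADT, if ADT does not affect the score, or if the two shares are equal. Its largest size is p × d, where p is the share of men whose ADT status differs between the two forms.

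**Range.** Section 1.2.1 says only that ADT suits some salvage patients and not others. Both p and d are therefore assumed.

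| p | d (SD) | Largest shift p × d (SD) |
|---|---|---|
| 0.10 | 0.2 | 0.02 |
| 0.25 | 0.5 | 0.125 |
| 0.50 | 0.5 | 0.25 |
| 0.50 | 1.0 | 0.50 |
| 0.80 | 1.0 | 0.80 |

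For scale, with an SD of change of 1, the standard error of a mean change is 1/√24 = 0.20 for a full arm and 1/√12 = 0.29 for 12 men.

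**Effect of the baseline form.** Assume p = 0.5, d = 0.5 and a true radiation change of −0.30 SD. Suppose every ADT man started more than a month before radiation and shows the full ADT effect by the pre-radiation form. Let f be the fraction of these men still on ADT at 24 months.

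- From the pre-ADT form: −0.30 − 0.25f
- From the pre-radiation form: −0.30 + 0.25(1 − f)

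| f | Pre-ADT form | Pre-radiation form |
|---|---|---|
| 0 | −0.30 | −0.05 |
| 0.5 | −0.425 | −0.175 |
| 1 | −0.55 | −0.30 |

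Either form returns −0.30 only when all these men follow one particular ADT course, and section 4.1 fixes no course.

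**Fitted model.** Section 8.4.3 does not state the form of time. Assume a straight line over forms at 0, 6, 12, 18 and 24 months, whose squared deviations from the mean of 12 sum to 144 + 36 + 0 + 36 + 144 = 360. Keep p × d = 0.25.

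- ADT effect at 0 and 6 months, then recovered: slope shift (12 × 0.25 + 6 × 0.25)/360 = 4.5/360. Over 24 months this is +0.30, so the fitted change is 0.00.
- ADT effect from after baseline through 24 months: slope shift (1.5 − 1.5 − 3)/360 = −3/360. Over 24 months this is −0.20, so the fitted change is −0.50.
- Half the ADT men on each course: +0.15 − 0.10 = +0.05, so the fitted change is −0.25.

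A simulation of the mixed model with 24 men, 12 of them on ADT, gave 0.00, −0.52 and −0.26. With a term for ADT status it gave −0.31, −0.32 and −0.31. In the first case the fitted shift (0.30) exceeds p × d (0.25) because of the assumed straight line.

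**The case against.** The strongest reply is that section 8.4.3 lists no fixed effects at all: not the form of time, not arm, not dose level. Leaving ADT out is then under-specification, and a reader who infers that the plan commits to pooling men with and without ADT goes beyond the text. That is right. It remains true that no instruction to separate them for these scores appears anywhere in the documents.

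The objective is also only to describe, with no test planned, and the protocol does not ignore ADT. Its use is recorded (6.1.1), testosterone is measured every three months, footnote 6 times questionnaires around it, and section 1.1.3 has an exploratory objective relating erectile-tissue MRI to testosterone and erectile dysfunction. This lowers the importance of the point. But the MRI work analyses imaging, and footnote 6 collects a form that section 8.4.3 does not say how to use.

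Three stronger readings are tempting and unsupported:

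- **The plan will overstate radiation harm.** The direction depends on ADT timing. Men on ADT at baseline who later recover push the result toward no harm, and opposite courses can nearly cancel (−0.25 against −0.30 above).
- **Section 5.1.4 shows that ADT drives SHIM.** It reports shrinkage of erectile tissue on another protocol, not questionnaire scores.
- **One pre-radiation form for all men would solve it.** Footnote 6 requires that extra form only when ADT began more than a month before radiation. For men starting later it asks only for a pre-ADT form, and section 2.5 does not clearly add another. A single named form could therefore be completed on ADT by some men and before ADT by others.

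**Conclusion.** The point holds as a minor improvement to a secondary, descriptive endpoint. With no ADT term, stratum or display, change in SHIM and the EPIC-26 sexual and hormonal domains would combine ADT and radiation effects. The size is up to p × d at a visit. The range of 0.02 to 0.80 SD rests wholly on assumed values, and the sign is unknown. At the upper end it exceeds the standard error for a full arm; at the lower end it is negligible.

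A reader might infer that the dose-finding result is affected. It is not: the MTD, escalation and sample size do not use these scores. Nor does the point extend to AUA-SI or the urinary and bowel domains, where the protocol cites evidence that ADT added no bowel or bladder toxicity.

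**What to change.** Add to section 8.4.3, for SHIM and the EPIC-26 sexual and hormonal domains:

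1. Report scores and changes descriptively by ADT use (with and without), as section 5.1.4 does for MRI. Show arm alongside, because "The use of ADT is dependent of specific tumor and patient characteristics" and the split may therefore follow disease status.
2. State which questionnaire is the baseline for men on ADT and flag whether it was completed before or on ADT. Where footnote 6 provides both forms, show change from each.
3. Interpret the erectile hypothesis as radiation alone only in men without ADT, and otherwise as radiation plus ADT.

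An ADT term in the mixed model (use, or testosterone at the visit) is an optional sensitivity analysis. Its precision cost depends on the ADT share. In simulation the standard error was 0.15–0.16 without the term and 0.14–0.18 with it for 24 men, half on ADT. With an ADT-by-time term, 48 men and 80% on ADT, it rose from 0.08 to about 0.18.

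The cost is SAP wording. ADT use, testosterone and the questionnaires are already collected, and patient care does not change. The downside is small, non-randomised subgroups. With an SD of change of 1, the standard error is about 0.29 SD with 12 men and 1/√6 = 0.41 SD with 6, so results by ADT use will be imprecise and should stay descriptive.
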